#### Reporting of Excluded Values

Individual values excluded as outliers will be documented in the final CSR. Approval of the final CSR will connote approval of the exclusion.

#### **10.3.2 Pharmacokinetic Statistical Methodology**

No formal statistical analysis is planned for this study. The PK parameters of donanemab will be listed and summarized by treatment using standard descriptive statistics.

## **10.4 Safety and Tolerability Assessments**

### **10.4.1 Adverse events**

Where changes in severity are recorded in the Case Report Form (CRF), each separate severity of the adverse event (AE) will be reported in the listings, only the most severe will be used in the summary tables. A pre-existing condition is defined as a condition that starts before the participant has provided written informed consent and is ongoing at consent. A non-treatment emergent AE is defined as an AE which starts after informed consent but prior to dosing. A TEAE is defined as an AE which occurs postdose or which is present prior to dosing and becomes more severe postdose.

All AEs will be listed. TEAEs will be summarized by treatment, severity and relationship to the study drug. The frequency (the number of AEs, the number of participants experiencing an AE and the percentage of participants experiencing an AE) of TEAEs will be summarized by treatment, Medical Dictionary for Regulatory Activities (MedDRA) version 25.0 (or later) system organ class and preferred term. The summary and frequency AE tables will be presented for all causalities and those considered related to the study drug by the investigator. Any serious AEs will be listed.

Discontinuations due to AEs will be listed.

### **10.4.2 Concomitant medication**

Concomitant medication will be coded using the world health organization (WHO) drug dictionary (Version B3 March 2022). Concomitant medication will be listed.

### **10.4.3 Clinical laboratory parameters**

All clinical chemistry and hematology data will be summarized by parameter and treatment together with changes from baseline, where baseline is defined as the Day -1 predose assessment, and listed. Urinalysis data will be listed. Additionally, clinical chemistry, hematology and urinalysis data outside the reference ranges will be listed and flagged on individual participant data listings.

### **10.4.4 Vital signs**

Vital signs data will be summarized by treatment and timepoint together with changes from baseline, where baseline is defined as the Day 1 predose assessment. Figures of mean vital signs and mean changes from baseline profiles will be presented by parameter and treatment.

Values for individual participants will be listed.

### **10.4.5 Electrocardiogram (ECG)**

ECGs will be performed for safety monitoring purposes only and will not be presented. Any clinically significant findings from ECGs will be reported as an AE.

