9.3. Statistical Analyses

9.3.1. General Considerations

Statistical analysis of this study will be the responsibility of Lilly or its designee.

Pharmacokinetic analysis may be conducted on data from participants who receive at least one dose of the study intervention and have evaluable PK data. Safety analyses will be conducted for all enrolled participants who receive study intervention, whether or not they completed all protocol requirements.

Summary statistics, data tabulations, and data graphs will be provided as deemed appropriate.

Additional exploratory analyses of the data may be conducted as deemed appropriate. Details of analyses will be fully documented in the SAP.

Handling of missing, unused, and spurious data are addressed prospectively in the overall statistical methods described in the protocol and in the SAP, where appropriate. Adjustments to the planned analyses are described in the final clinical study report.

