9.3.2. Primary Endpoint Analysis

The primary endpoint is the incidence of TEAEs and SAEs events to investigate the safety and tolerability of donanemab versus placebo following IV administration of single dose in Chinese healthy participants.

The statistical evaluation of safety will be listed and/or summarized by treatment group.

All study intervention and protocol procedure AEs will be listed, and if the frequency of events allows, safety data will be summarized using descriptive methodology.

Safety parameters that will be assessed include safety laboratory parameters, vital signs, and ECG parameters. Safety parameters will be listed and summarized using standard descriptive statistics as appropriate.

The incidence of symptoms for each treatment will be presented by severity and by association with the study intervention as perceived by the investigator. Symptoms reported to have occurred prior to randomization will be distinguished from those reported as new or increased in severity during the study. Each symptom will be classified by the most suitable term from the Medical Dictionary for Regulatory Activities.

The number of TEAEs and SAEs will be reported.

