### **3. INTRODUCTION**

This SAP has been developed after review of the Clinical Study Protocol (final version dated 11 Jan 2022) and protocol amendment (a) dated 17 Jun 2022.

This SAP describes the planned analysis of the safety, tolerability and pharmacokinetic (PK) data from this study. A detailed description of the planned TFLs to be presented in the clinical study report (CSR) is provided in the accompanying TFL shell document.

The intent of this document is to provide guidance for the statistical and PK analyses of data. In general, the analyses are based on information from the protocol, unless they have been modified by agreement with Eli Lilly and Company. A limited amount of information concerning this study (e.g., objectives, study design) is given to help the reader's interpretation. This SAP must be finalized prior to unblinding. When the SAP and TFL shells are agreed upon and finalized, they will serve as the template for this study's CSR.

This SAP supersedes the statistical considerations identified in the protocol; where considerations are substantially different, they will be so identified. If additional analyses are required to supplement the planned analyses described in this SAP, they may be performed and will be identified in the CSR. Any substantial deviations from this SAP will be agreed upon with Eli Lilly and Company and identified in the CSR. Any minor deviations from the TFLs may not be documented in the CSR.

This SAP is written with consideration of the recommendations outlined in the International Conference on Harmonisation (ICH) E9 Guideline entitled Guidance for Industry: Statistical Principles for Clinical Trials and the ICH E3 Guideline entitled Guidance for Industry: Structure and Content of Clinical Study Reports.

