### **12. CHANGES FROM THE PROTOCOL SPECIFIED STATISTICAL ANALYSES**

There were no changes from the protocol specified statistical analyses.

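### SAP 10.4.5 drops the ECG listing and summary that Protocol 9.3.2 plans, while SAP 12 declares no change

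*SAP*

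**What the plan says.** Protocol 9.3.2, the primary endpoint analysis section, states: "Safety parameters that will be assessed include safety laboratory parameters, vital signs, and ECG parameters". It continues: "Safety parameters will be listed and summarized using standard descriptive statistics as appropriate". The same section says the safety evaluation will be listed, summarised, or both, by treatment group. Protocol 8.2.3 has heart rate, PR, QRS and QT obtained from each single 12-lead ECG.

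SAP 10.4.5 states: "ECGs will be performed for safety monitoring purposes only and will not be presented". It adds only that clinically significant findings become AEs.

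On departures from the protocol, SAP 3 says "This SAP supersedes the statistical considerations identified in the protocol" and then "where considerations are substantially different, they will be so identified". SAP 12 reads, in full: "There were no changes from the protocol specified statistical analyses".

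**The concern.** The protocol treats three kinds of safety measurement alike. The SAP keeps outputs for two of them and removes all output for the third, then says nothing has changed.

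Safety and tolerability versus placebo is the primary objective. If the SAP is followed as written, the clinical study report will summarise chemistry, hematology and vital signs by treatment, list urinalysis, and show no ECG value at all. The only ECG information reaching a reader will be findings that an investigator considered clinically significant. A modest shift in an interval across dose groups, with no single tracing striking enough to be reported, could not be seen. A reader relying on SAP 12 would have no signal that a planned output had been removed.

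**Working it through.** The plan gives no ECG count to reproduce, and the point rests mainly on comparing text. The arithmetic only sizes what is left out.

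**Comparison of the texts**

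1. *Planned output.* Protocol 9.3.2 names ECG parameters and says safety parameters are listed and summarised, with a qualifier of appropriateness at the end of the sentence.
2. *SAP output for the three named classes.* Vital signs (SAP 10.4.4): summarised by treatment and timepoint, and listed. Laboratory (SAP 10.4.3): chemistry and hematology are summarised and listed; for urinalysis, "Urinalysis data will be listed". ECG (SAP 10.4.5): neither.
3. *What the qualifier covers.* Urinalysis shows the SAP using its latitude to drop a summary while keeping the listing. The ECG section drops both. The protocol's by-treatment sentence offers listing, summary or both, and presenting neither satisfies no part of it.
4. *Whether another SAP section restores the listing.* SAP 10.4.12 lists only assessments not detailed in Section 10.4, and ECGs are detailed there, so it does not apply. SAP 10.1 promises a listing of everything databased. The documents do not show whether ECG values are databased: Protocol 8.2.3 says only that recordings are stored at the CRU. If they are databased, SAP 10.4.5 and SAP 10.1 also need reconciling.
5. *Whether the difference is declared.* SAP 10.4.5 states the decision but does not call it a departure. SAP 12 says there is none.

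**Size of the omission**

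Inputs: the ECG row of the Schedule of Activities (Protocol 1.3), and the cohort sizes and 5:1 ratio (Protocol 4.1).

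- ECGs per participant: screening 1 + Day 1 at 0 h and 6 h 2 + Day 2 (24 h) 1 + Day 5 1 + Day 29 1 + Day 85 1 = 7.
- Post-dose: 6 h, 24 h, Days 5, 29 and 85 = 5. The 0 h recording is taken before dosing.
- Per cohort of 12 at 5:1: 12 × 5/6 = 10 donanemab and 2 placebo. Over three cohorts: 10 at each dose and 3 × 2 = 6 placebo.
- All scheduled ECGs: 36 × 7 = 252.
- Post-dose: 36 × 5 = 180, made up of placebo 6 × 5 = 30 and three doses at 10 × 5 = 50 each (150).

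These are scheduled maxima for 36 participants. Counting only the approximately 30 planned completers gives 30 × 7 = 210 in all and 30 × 5 = 150 post-dose. The Day 29 label should be checked against the table layout in the protocol; the counts do not depend on it.

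**The case against.** The best defence is that the protocol delegated this choice. Protocol 9.3.1 provides summaries, tabulations and graphs as deemed appropriate and leaves the detail to the SAP. The qualifier in 9.3.2 closes a sentence that covers listing as well as summarising. On that reading SAP 10.4.5 uses a discretion it was given. It does so openly, under its own heading and with a reason, and SAP 12 is not false. SAP 3 asks for identification only of substantial differences, does not define them, and does not say they must appear in Section 12. Protocol 9.3.1 also says "Adjustments to the planned analyses are described in the final clinical study report". Finally, little is lost: no ECG measure is an endpoint, no inference is planned, placebo has 6 participants, significant findings enter the AE outputs, and Protocol 8.2.6 keeps periodic sponsor review of ECGs.

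Much of this stands as a limit on importance. The discretion can excuse a missing summary, and the omission is not hidden. It does not carry the whole case. Removing all output for one of three named classes is more than choosing among summaries, and the by-treatment sentence expects at least one form of presentation. A later description in the study report does not make the SAP 12 sentence accurate, and a SAP that declares no change gives the report's authors nothing to carry forward.

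**Conclusion.** The concern holds and should be fixed. SAP 10.4.5 removes both the listing and the by-treatment description of a parameter class that Protocol 9.3.2 plans to present, and SAP 12 wrongly reports no change. Up to 252 scheduled ECGs, 180 of them post-dose, would contribute no presented value.

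The loss is confined to the description of heart rate, PR, QRS and QT. No endpoint, estimate or AE output changes. The conclusion rests on reading the protocol's qualifier as not extending to removal of the listing as well as the summary. The counts assume 36 participants attending every scheduled ECG. The possible conflict with SAP 10.1 is conditional on ECG values being databased, which the documents do not establish; the main conclusion does not need it.

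**What to change.** Preferred route: replace SAP 10.4.5 with text such as:

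> Heart rate, PR, QRS and QT will be listed, and summarised by treatment and timepoint with change from the Day 1 predose value. QTc will be included only if derived by a formula named in this SAP. Clinically significant findings will also be reported as AEs.

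The timepoint layout and Day 1 predose baseline follow what SAP 10.4.4 already does for vital signs; Protocol 9.3.2 does not itself specify them. Cost: the SAP wording, one listing and one table. If ECG values are not databased, add CRF fields and entry of up to 252 records. No participant undergoes any new procedure.

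Alternative, if the sponsor keeps the omission: replace the SAP 12 sentence with:

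> Protocol 9.3.2 plans listing and, as appropriate, summary of ECG parameters. ECG values will not be presented because [reason]. Clinically significant findings are reported as AEs.

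If the values are databased, SAP 10.1 must also state the ECG exception. Cost: one entry in SAP 12 and, where needed, one exception in SAP 10.1.

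Either route removes the undeclared difference. Only the first restores the ECG description under the primary safety objective.

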#### **10.4.6 Hepatic Monitoring**

Hepatic monitoring will be performed as outlined in Section 8.2.6.2. of the protocol.

Where applicable, the following will be presented. The participants' liver disease history and associated person liver disease history data will be listed. Use of acetaminophen during the study, which has potential for hepatotoxicity, will be listed. Results from any hepatic monitoring procedures, such as a magnetic resonance elastography scan, and biopsy assessments will be listed, if performed.

Hepatic risk factor assessment data will be listed. Liver related signs and symptoms data will be summarized by treatment and listed. Alcohol and recreational drug use data will also be listed.

All hepatic chemistry, hematology, coagulation, and serology data will be listed. Values outside the reference ranges will be flagged on the individual participant data listings.

#### **10.4.7 Immunogenicity Assessments**

Immunogenicity data will be listed and frequency tables will be presented if analysed. The frequency and percentage of participants with pre-existing antidrug antibody (ADA) and with TE-ADAs will be presented by treatment. TE-ADAs are defined as those with a titer 2-fold (1 dilution) greater than the minimum required dilution if no ADAs were detected at baseline (treatment-induced ADA) or those with a 4-fold (2 dilutions) increase in titer compared to baseline if ADAs were detected at baseline (treatment-boosted ADA), where baseline is defined as Day 1 predose.

The frequency and percentage of participants with neutralizing antibodies, if measured, may also be tabulated for participants with TE ADA.

#### **10.4.8 Hypersensitivity reactions**

For all drug hypersensitivity reactions that occur, additional follow-up data will be collected to assess the patient's medical history, alternative causes, and symptoms.

These data will be listed.

#### **10.4.9 Neurological Examination**

A directed neurological examination will be performed by the investigator at the time points specified in the protocol. If clinically significant abnormalities are noted at these time points, additional examinations should be performed as clinically necessary. The examiner should be familiar with the participant's baseline examination. Elements of the examination may include inspection for tremor, extraocular movements, brachial and patellar deep tendon reflexes, finger-nose pointing, and Romberg sign.

The below table presents the scoring of the neurological examination findings.

Score	0	1	2	3	4
Tremor	Absent	Visible with limb extension and/or careful inspection	Visible without limb extension	Interferes with motor function	
Nystagmus	Absent	1 to 3 beats on lateral gaze	>3 beats on lateral gaze	Present on forward gaze	
Reflexes (brachial or patellar)	Normal	Trace	Absent	Increased	Clonic
Finger-nose	Normal	Abnormal			
Romberg sign	Absent	Present			

The frequency of neurological survey data will be summarized by treatment and timepoint, and listed.

#### **10.4.10 Infusion-Related Reactions**

Infusion-related reaction data will be listed and summarized by treatment in frequency tables.

#### **10.4.11 Pharmacogenetic Samples**

Pharmacogenetic data for apolipoprotein E genotype ε4 carrier status will be listed.

#### **10.4.12 Other assessments**

All other safety assessments not detailed in this section will be listed but not summarized or statistically analyzed.

#### **10.4.13 Safety and Tolerability Statistical Methodology**

No inferential statistical analyses are planned.

### **11. INTERIM ANALYSES**

No interim statistical analyses are planned.

### **12. CHANGES FROM THE PROTOCOL SPECIFIED STATISTICAL ANALYSES**

There were no changes from the protocol specified statistical analyses.

## **14. DATA PRESENTATION**

### **14.1 Derived Parameters**

Individual derived parameters (e.g. PK parameters) and appropriate summary statistics will be reported to three significant figures. Observed concentration data, e.g.  $C_{max}$ , should be reported as received. Observed time data, e.g.  $t_{max}$ , should be reported as received. Number of observations and percentage values should be reported as whole numbers. Median values should be treated as an observed parameter and reported to the same number of decimal places as minimum and maximum values.

### **14.2 Missing Data**

Missing data will not be displayed in listings.

### **14.3 Insufficient Data for Presentation**

Some of the TFLs may not have sufficient numbers of participants or data for presentation. If this occurs, the blank TFL shell will be presented with a message printed in the center of the table, such as, “No serious adverse events occurred for this study.”

